11.1 Treatment groups and Investigational Medical Product (IMP)

Treatment groups are defined according to initial actual treatment received as placebo, Evobrutinib 25 mg QD, Evobrutinib 75 mg QD, Evobrutinib 75 mg BID, and Tecfidera. All participants who choose to continue the OLE period entered on the 75 mg once daily dose and have switched to the 75 mg twice daily dose following protocol amendment V5 dated 21 November 2018. Unless otherwise indicated, all analyses will be presented separately for the 5 initial treatment groups plus combined across treatment groups (i.e., "Total"). The IMP during the OLE phase is Evobrutinib.

11.2 Presentation of Tables/Listings/Figures

TLFs will be presented using initial treatment groups (i.e., true treatment groups as "Placebo+Evobrutinib 25 mg QD", "Evobrutinib 25 mg QD", "Evobrutinib 75 mg QD", "Evobrutinib 75 mg BID", and "Tecfidera") and total population. A footnote will be added to indicate that participants switched from Placebo to Evobrutinib 25 mg QD for the second 24-week treatment period. A second footnote will be added to indicate that all participants switched to Evobrutinib 75 mg QD on OLE Week 0 and following protocol amendment V5 dated 21 November 2018, all participants still ongoing in OLE switched to Evobrutinib 75 mg BID.

All data recorded during the trial will be presented in individual data listings performed on the Safety OLE Analysis Set (SAF-OLE), unless otherwise specified. All listings will be sorted by treatment group, participant, and scheduled time point (where applicable), if not otherwise stated. Further details are provided in the appropriate section for the analysis of the specific parameter.

Tables and figures will be presented by treatment group and scheduled time point during OLE period (where applicable), unless otherwise specified. Tables and figures will be sorted by treatment group and chronological scheduled time point (where applicable).

Summary statistics as displayed in tables and figures will include data until end of study.

11.3 Presentation by Time Period

Tables summarizing data from the overall OLE study period will be provided, unless otherwise specified.

Boxplots for laboratory parameters will be split in several periods to remain readable.

Some outputs will be split between the OLE period where the participants are taking 75 mg QD and the period where the participants are taking 75 mg BID.

Listings will be presented for both DBP and OLE period depending on the corresponding table or figure. All listings with assessments during OLE period will have a flag indicating either the first

visit where the switch to Evobrutinib 75 mg BID occurred, or all the events occurring on or after the date of the switch.

11.4 Data handling after cut-off date

Not applicable.

11.5 Presentation of continuous and qualitative variables

Continuous variables will be summarized using descriptive statistics, i.e.:

- number of participants (N)
- number and percentage of non-missing values
- number and percentage of missing values.
- mean, standard deviation (SD)
- median, 25th Percentile 75th Percentile (Q1-Q3)
- minimum, and maximum

The number of digits for non-derived and derived data, presented in outputs or available in ADaM (Analysis Data Model) datasets, is specified in the Biostatistics Outputs Assembly (BOA) document.

For both continuous and qualitative variables, percentages as 0% or 100% should be reported with the same format used for the column and together with the count of values. For example, if the count of value is zero, then display '0 (0.0)'; if the percentage is 100% then display 'xx (100.0)'.

Qualitative variables will be summarized by counts and percentages. A missing category should always be displayed at baseline – even when no missing data. A missing category, at other endpoints than baseline, should only be displayed when there are missing data.

Unless otherwise stated, the calculation of proportions will be based on the number of participants in the analysis set of interest. Therefore, counts of missing observations will be included in the denominator and presented as a separate category.

In case the analysis refers only to certain visits, percentages will be based on the number of participants in the analysis set of interest, unless otherwise specified. Total of missing and non-missing observations at each time-point will reflect the population still in the trial at that time. For example, if a participant is still in the trial at the time-point but with missing data, it should be counted in the number of missing observations.

11.6 Definition of baseline and change from baseline

For the purpose of statistical analysis, OLE baseline is defined as the last non-missing measurement (including those collected at an Unscheduled visit) prior to the first dose of IMP during OLE. Study baseline is defined as the last non-missing measurement (including those

collected at an Unscheduled visit) prior to the first dose of IMP in the study. If baseline cannot be defined, then the baseline value will be treated as missing. OLE baseline will be used in OLE tables and both baselines will be displayed in the listings based on DBP+OLE period, unless otherwise specified.

Definition of change from baseline (CFB)

CFB and percent CFB at a given post-baseline visit will be computed as follows:

- CFB = visit value baseline value
- Percent CFB = 100 * (visit value baseline value) / baseline value

At the baseline visit, the CFB will be equal to zero and the percent CFB will be missing.

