[figure not shown]

Figure 2 Trial Design – Optional OLE Period

BID=twice a day; D=Day; IMP= investigational medicinal product; MRI=magnetic resonance imaging; OLE=Open-label Extension; QD=once a day.

- a Participants who entered the OLE Period initially received M2951 at 75 mg once daily. After review of the efficacy and safety data from the primary analysis at 24 weeks and the blinded extension analysis at 48 weeks, the optimal tested dose is 75 mg twice daily. Accordingly, once IMP for this dose is available at the study site, participants participating in the OLE Period will either enter the OLE Period on the 75 mg twice daily dose or will be switched to the 75 mg twice daily dose.
 - For participants entering the OLE after receiving M2951 during the 48-week main study, the Week 48 Visit is considered the Day 1 Visit for the OLE period.
- b For participants entering from Tecfidera treatment arm, treatment with M2951 will only commence if a participant who received Tecfidera during the 48-week main study has an absolute lymphocyte count ≥ 800/mm³ following 4 weeks of washout. If the participant does not have an absolute lymphocyte count ≥ 800/mm³ following 8 weeks of washout, he or she will be discontinued from the study.
- c Denotes efficacy visits only. Safety visits will be conducted every 2 weeks during the first 16 weeks of treatment, then monthly during the OLE period until Week 96, then 3-monthly until Week 192, then 6-monthly until Week 384.
- d An interim analysis will be performed at Week 60 of the OLE period. A further interim analysis will be planned at the appropriate time point considering the visits schedule around the time of the trigger for the primary analysis of the Phase III RMS studies.
- e Between Week 96 and Week 384 regular Telephone Visits will occur. See Table 3 for the schedule and Section 7.1.6.1 for details of the Telephone Visits.

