17.2.3 TEAEs of Special Interest

The following events are defined as AEs of Special Interest (AESI):

- Liver related AEs
- Infections:
 - All Infections reported as Serious AEs or Grade ≥ 3
 - All opportunistic infections
- Amylase and lipase elevations including acute pancreatitis
- Seizures

AESI will be identified using Standardized MedDRA query (SMQ) if available or sponsor-defined list of search term (refer to Appendix 19.5). AESI terms will be summarized under all categories they fall under.

An overview of AESI will be presented by treatment group showing number and percentage of participants experiencing AESI for the OLE period. Study intervention related AESI will also be presented. AESIs will be flagged in the AE listings.

Additional analysis on the infections will be performed.

The following output will be provided:

Kaplan-Meier figure for time to onset of infections. An event is defined as first occurrence of any PT in the SMQ "Severe Infections" or AESI "Opportunistic infections" from first day of exposure with Evobrutinib (i.e. for patients in the Placebo and Tecfidera groups the time period starts after switch to Evobrutinib 25 mg QD (week 25) and switch to Evobrutinib 75 mg QD, respectively. For all other patients the time period starts at study start (with first intake of Evobrutinib)). An overall Kaplan-Meier curve will be displayed.

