17.3 Clinical Laboratory Evaluation

The clinical laboratory safety parameters measured in this trial and reported as part of the safety evaluation of hematology, biochemistry, and urinalysis, are specified in the protocol (Table 8 of the Clinical Trial Protocol, Section 7.4.3). The entire clinical laboratory section will be analyzed for OLE period. Some outputs not produced at time or Primary analysis and Blinded Extension analysis will also be repeated on the DBP for participants of the SAF analysis set.

Summaries of Clinical Laboratory Data

Laboratory values (including corresponding normal ranges) converted in standard units will be used for summary statistics, shift tables and boxplots. Gradable laboratory results will be classified according to the grades defined in NCI-CTCAE Version 4.03 as provided by the central laboratory. If a laboratory parameter has bi-directional toxicities (e.g., Potassium), both directions will be presented for the given parameter (i.e., Potassium Low and Potassium High). On-treatment values are defined as results of assessments made after the first IMP administration on Day 1. Laboratory results containing a modifier such as "<" or "\ge " will be handled case by case for summary statistics and will be reported both as collected in the database and as imputed in participant data listings. Data until the Safety Follow-up included will be used to derive the worst on-treatment values.

All parameters will also be presented according to the categories based on normal ranges: below normal limits (Low), within normal limits (Normal) and above normal limits (High).

Shift tables of baseline value (low, normal, high) versus worst on-treatment value, presented by treatment group, will be provided for hematology and biochemistry parameters.

Shift tables of baseline grade versus worst post-baseline grade, presented by treatment group, will be provided for hematology and biochemistry parameters.

Shift tables will be displayed using the OLE Baseline and worst on-treatment value or worst post-baseline grade during OLE period.

Directional laboratory tests (hematology, biochemistry) (Appendix 19.1) will be summarized by worst on-treatment value and by treatment group.

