17.4 Vital Signs

The SAF-OLE analysis set will be used in presenting the vital signs results. Vital signs (height (cm), weight (kg), BMI (kg/m²), body temperature (°C), Systolic Blood Pressure (SBP) (mmHg), Diastolic Blood Pressure (DBP) (mmHg), respiratory rate (breaths/min) and pulse rate (beats/min)) will be summarized by treatment group using descriptive statistics (see Section 11.5).

The descriptive statistics will be presented as follows:

- · The OLE baseline will be presented first
- Then each scheduled time point will be presented on participants who have reached this time
 point: absolute values and OLE CFB will be displayed (except for height and BMI as they are
 only present at screening visit).

Body temperature, SBP, DBP, respiratory rate and pulse rate will be analyzed with shift tables of maximum CFB using the categories defined in Table 5:

Table 5: Vital Signs Categories

Parameter	Unit	Shift	Baseline categories	Post-baseline categories (absolute change)
Temperature	°C	Increase	<37 / ≥37 - <38 / ≥38 - <39 /≥39 - <40 / ≥ 40	≤0* / >0 - <1 / ≥1 - <2 /≥2 - <3 / ≥3
Pulse rate	1 '	Increase and decrease	<100 / ≥100	≤0*/>0 - ≤20/>20 - ≤40/>40
SBP	9	Increase and decrease	<140 / ≥140	≤0* / >0 - ≤20 / >20 - ≤40 / >40
DBP		Increase and decrease	<90 / ≥90	≤0*/>0-≤20/>20-≤40/>40
Respiratory rate		Increase and decrease	<20 / ≥20	≤0* / >0 - ≤5 / >5 - ≤10 / >10

^{*} This category will include the participants with no changes or decrease/increase in the increase/decrease part of the table respectively.

In addition, 2 scatter plots on OLE period will be provided presenting:

- OLE baseline SBP value versus maximum (highest) post-baseline SBP value
- OLE baseline Diastolic BP value versus maximum (highest) post-baseline Diastolic BP value

Line for linear regression will be included. The figures will be produced overall, i.e., for all participants pooled.

A listing of maximum CFB for OLE period and a listing of all vital signs data for OLE period will be provided.

17.5 12-Lead Electrocardiogram (ECG)

The 12-lead ECG data will be listed and summarized for the OLE period for observed values and change from OLE baseline values by treatment group using descriptive statistics:

- Ventricular rate (beats/min)
- Pulse rate interval (msec)
- QRS (msec)
- QT (msec)
- Fridericia corrected QT (QTcF) (msec).

The QTcF parameter will be categorized by observed value into the categories

- \leq 430 msec,
- > 430 450 msec,
- > 450 480 msec.
- > 480 500 msec,

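### The OLE laboratory, vital-sign and QTcF change tables have no pre-evobrutinib reference for four of the five groups

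*SAP*

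**What the plan says.** SAP 11.6 defines OLE baseline as the last non-missing measurement "prior to the first dose of IMP during OLE" and sets the default: "OLE baseline will be used in OLE tables and both baselines will be displayed in the listings". The second half applies to listings that span the double-blind period and the OLE, and the whole rule gives way where another section specifies otherwise.

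The safety sections follow that default:

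- Laboratory (SAP 17.3): "Shift tables will be displayed using the OLE Baseline and worst on-treatment value or worst post-baseline grade during OLE period". By-visit observed and change values are also tabulated for the OLE.
- Vital signs (SAP 17.4): absolute values and change from OLE baseline by visit, plus shift tables of maximum change.
- ECG (SAP 17.5): data are "summarized for the OLE period for observed values and change from OLE baseline values by treatment group". QTcF change is grouped as up to 30, above 30 to 60, and above 60 msec.

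On exposure before the OLE, Protocol 5.1 (Figure 2 notes) says that for participants coming from M2951 "the Week 48 Visit is considered the Day 1 Visit for the OLE period". SAP 11.2 footnotes that "participants switched from Placebo to Evobrutinib 25 mg QD for the second 24-week treatment period". Protocol 5.5.1 requires at least 4 weeks of washout for participants coming from Tecfidera. SAP 11.1 shows results for the five initial groups side by side and combined as Total.

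Elsewhere the SAP uses a different origin. The infection curve in 17.2.3 runs "from first day of exposure with Evobrutinib". Two ALT curves in 17.3 also start at the first evobrutinib dose, and the C-SSRS shifts in 17.10 are shown from study baseline as well as OLE baseline.

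**The concern.** The OLE objective is long-term safety on M2951. A change or shift table is normally read as change since treatment began. Here it means change since OLE entry, which for most participants is change after 24 or 48 weeks on the drug. A sustained shift that developed by Week 48 sits in the baseline row and is not counted as a shift. A gradual change is cut in two at OLE entry, and no specified table puts the halves together within a participant for laboratory, vital-sign or ECG data.

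The columns also differ in meaning. In the former Tecfidera column, change from OLE baseline includes the first response to evobrutinib; in the other four it does not. Total averages the two kinds.

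Two OLE-only curves in SAP 17.3 have a related limit. The ALT grade 2 or higher curve takes only participants below grade 2 at OLE baseline, and the eGFR below 60 curve takes only those at 60 or above. Anyone who crossed the threshold in the main study and stayed there is left out of both the risk set and the events.

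**Working it through.** **1. Exposure at OLE baseline, by group** (Protocol 5.1 and 5.5.1; SAP 11.2)

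| Initial group | Evobrutinib before OLE baseline | OLE baseline |
|---|---|---|
| 25 mg QD, 75 mg QD, 75 mg BID | 48 weeks | on drug |
| Placebo, then 25 mg QD | 24 weeks | on drug |
| Tecfidera | none (washout) | evobrutinib-naive |

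Four of five groups have an on-drug OLE baseline.

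**2. Participants.** Protocol 8.1 expects 250 × 0.80 = 200 in the OLE, which reproduces its stated figure. Assuming equal continuation by group, 200 × 4/5 = 160 have an on-drug OLE baseline and 200 × 1/5 = 40 do not.

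**3. Is a pre-evobrutinib comparison available elsewhere?** No table gives it for OLE laboratory, vital-sign or ECG values. The listings mostly do not either: the vital-sign and ECG listings and the full laboratory listing cover the OLE only. The exceptions are the listings of Grade 3 or higher laboratory values, which cover both periods, and the liver-test listing for participants with an elevation, which shows change from both baselines.

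**4. A threshold split across periods.** Take a hypothetical QTcF rise of 35 msec in the main study and a further 30 msec in the OLE. The OLE table places the 30 in its lowest change category. The total, 35 + 30 = 65 msec, belongs in the category above 60, but no specified OLE table computes it.

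**5. How much change is absorbed?** The documents give no onset time, so this is an illustration over a range. Assume a constant dose and exponential onset with half-life h weeks, and look at OLE Week 240. With p weeks of earlier exposure, the share already inside OLE baseline is

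(1 − 2^(−p/h)) / (1 − 2^(−(p+240)/h)).

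For p = 48 and h = 24: (1 − 2^(−2)) / (1 − 2^(−12)) = 0.75 / 0.9998 = 75%.

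| Assumed half-life (weeks) | Absorbed, p = 48 (evobrutinib arms) | Absorbed, p = 24 (placebo arm) | Still visible, mean of five columns |
|---|---|---|---|
| 4 | 100% | 98% | (3×0.0 + 1.6 + 100)/5 = 20% |
| 12 | 94% | 75% | (3×6.2 + 25.0 + 100)/5 = 29% |
| 24 | 75% | 50% | (3×25.0 + 50.0 + 100)/5 = 45% |
| 48 | 51% | 30% | (3×49.2 + 70.0 + 100)/5 = 64% |

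The last column gives the former Tecfidera group 100%. Fast-onset effects are largely absorbed; slow-onset effects only in part. Any extra effect of the higher OLE dose in the lower-dose groups would raise the visible share.

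**The case against.** The strongest defence is that the choice is permitted and coherent. Protocol 8.5.1 leaves baseline definitions to the analysis plan. The OLE objective concerns 75 mg once daily, then twice daily, so for the two groups that were on 25 mg, OLE baseline isolates the added change at the OLE dose. It also matches the first-OLE-dose reference date for OLE TEAEs in SAP 17.1. Main-study change belongs to the Primary and Blinded Extension analyses. This stands as a reason to keep the OLE-baseline tables. It does not supply cumulative change, because the earlier analyses stop at Week 24 and Week 52.

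A reader might infer something stronger: that any effect arising in the first 24 to 48 weeks vanishes from the long-term safety outputs. The documents do not support that. These remain:

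- observed values by visit, laboratory boxplots and worst on-treatment summaries;
- AST, ALT and bilirubin multiples of ULN, and eDISH plots;
- absolute QTcF categories;
- the ALT, infection and potential-DILI outputs that include main-study exposure;
- immunoglobulin percent-change plots over both periods (the SAP says only baseline there, without saying which);
- C-SSRS shifts from study baseline.

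A shift table also prints the baseline grade, so someone at Grade 2 throughout the OLE is visible as Grade 2 at entry, though not as a change on drug.

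Replacing OLE baseline as the primary reference would bring its own mismatch. At OLE Week 48, time since the first evobrutinib dose would be 48 + 48 = 96 weeks in the evobrutinib arms, 24 + 48 = 72 in the placebo arm and 48 in the Tecfidera arm. That objection stands, and it is why an added display is preferable to a replacement.

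**Conclusion.** The point holds for the OLE laboratory shift and change tables, the vital-sign change tables and the QTcF change categories. They lack a pre-evobrutinib reference for four of five groups, about 160 of 200 expected participants under equal continuation. They understate cumulative change that began in the main study, and they pool unlike baselines in Total.

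The documents do not fix the size of the understatement. One might infer that an early effect shows as zero in four columns and as 20% of its size in Total. That needs full onset before OLE entry and an equal effect at every dose, and neither is stated. Under the half-lives assumed above, 51% to 100% is absorbed in the evobrutinib arms and 30% to 98% in the placebo arm, before allowing for the dose increase.

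This is a gap in presentation, inexpensive to close. It is not an error that invalidates the safety analysis.

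**What to change.** Keep the OLE-baseline tables. Add a parallel version of the laboratory shift and change tables, the vital-sign change tables and the QTcF change-category table, referenced to the last value before the first evobrutinib dose:

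- the three evobrutinib arms: study baseline;
- placebo: the last value before the switch, around Week 24, or the latest earlier value if that visit is missing;
- Tecfidera: OLE baseline.

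Footnote that time since first evobrutinib dose differs by column. The two OLE-only curves can stay: participants they exclude who remain past the threshold would be visible in the parallel shift tables. Changes that arose and resolved within the main study would still be seen only in the main-study outputs.

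No new data are needed. Protocol Table 1 schedules laboratory, vital-sign and ECG assessments at Screening and Week 24, and Protocol 7.1.2 places visit assessments before dosing. SAP Appendix 3 already uses the time of first evobrutinib exposure in the second 24-week period to set its main-study biochemistry windows. The work is one extra baseline flag and a second run of existing tables; the downside is more output pages.

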11.7 Definition of duration

Duration will be calculated as the difference between start and stop dates plus 1 (e.g., AE duration (days) = AE end date - AE start date + 1).

The time since an event will be calculated as:

- reference date minus date of event +1 (eg, days in study at onset of AE = AE start date date of randomization + 1) if date of event is equal or greater than reference date
- reference date minus date of event (eg, days in study at onset of AE = AE start date date of randomization) otherwise.

11.8 Conversion factors

The following conversion factors will be used to convert days into months or years: 1 month = 30.4375 days, 1 year = 365.25 days.

11.9 Handling of missing data

Unless otherwise specified, missing data will not be replaced.

In all participant data listings, imputed values will be presented and flagged. Partial dates, which are not to be imputed according to this IAP, will be presented using the format "____YYYY".

Missing statistics, eg, when they cannot be calculated, should be presented as 'nd', with 'nd' standing for 'not done'. For example, if n = 1, the measure of variability (SD) cannot be computed and should be presented as 'nd'.

In case of zero records available for presentation in a given TLF, then an empty output with 0 occurrence or a sentence stating that there are no data will be provided. For tables of Adverse Events and Deaths (outputs required for EudraCT and/or clinicaltrial.gov), if there is no observation, the output must contain the first line 'Participant with...' or 'Participant who died' displayed with 0 occurrence.

If a System Organ Class (SOC) or Anatomical Therapeutic Class (ATC) term is missing/not coded yet, then 'Uncoded SOC' (or 'Uncoded ATC') will be indicated at the TLF level. When a Preferred Term (PT) is missing, it will be set to 'Uncoded PT:' TEAE verbatim text.

Incomplete AE-related dates will be handled as follows:

- In case the onset date is missing completely or missing partially but the onset month and year, or the onset year, are equal to the start of IMP, then the onset date will be replaced by the minimum of the start of IMP date and the AE resolution date (if not missing).
- In all other cases the missing onset day or missing onset month will be replaced by 1.
- Incomplete stop dates will be replaced by the last day of the month (if day is missing only), if not resulting in a date later than the date of participant death. In the latter case, the date of death will be used to impute the incomplete stop date.

Participants with study termination e-CRF form completed and treatment termination form missing at the time of the end of study will be handled as follows:

End of treatment status will be set to "Discontinued" and the following end of treatment information will be carried over from the study termination e-CRF form:

- Reason for discontinuation of treatment will be replaced by the reason for study discontinuation
- Reason for discontinuation of treatment protocol non-compliance/withdrawal of consent/Other, specify free-text fields will be replaced by the corresponding free-text fields in the study termination form
- End of treatment date will be replaced by the discontinuation date from the study termination e-CRF form

